A randomized, double-blind, comparative, effectiveness and safety study of Elevi[®] vs. Hetastarch in subjects undergoing Endoscopic Mucosal Resection (EMR) of colonic lesions equal to or larger than 11mm

NCT03350217

A randomized, double-blind, comparative, effectiveness and safety study of Eleview vs. Hetastarch in subjects undergoing Endoscopic Mucosal Resection (EMR) of colonic lesions equal to or larger than 11mm

Primary Investigator:

[name],
Indiana University Hospital
Indianapolis, IN 46202

Introduction:

EMR is a technique used for the removal of flat or sessile neoplasms confined to the superficial layers of the GI tract using a snare. Injection-assisted EMR is commonly used during resections of larger flat lesions as it provides submucosal lift of polyps, adenomas, other gastrointestinal mucosal lesions or early-stage cancers prior to EMR. This has been found to minimize mechanical or electrocautery damage to the deep layers of the gastrointestinal tract wall as the injectate provides a “safety cushion” as such between the area to be removed and healthy mucosal tissue (ASGE, 2008).

Several solutions are used today for injecting lesions including saline, hyaluronic acid, and hydroxyethyl starch (Hetastarch). Saline solution has been found to dissipate within minutes, which may result in a lower quality lesion lift.

Hyaluronic acid provides a longer lift, but is expensive and is not readily available in the U.S (Hwang, 2015).

A new injectate known as Eleview has been developed for use in gastrointestinal endoscopic procedures and recently approved by the FDA. This injectate boasts a cushion of excellent height and duration through the use of an oil-in-water emulsion. However the initial cost of this material is quite high (\$80 per 10 ml). Hetastarch, which is the current injectate used by [name], is a safe and considerably inexpensive solution that provides prolonged submucosal elevation and lowers procedure times (Fasoulas, 2012). Our study will aim to compare Eleview to Hetastarch in the hopes of finding the ideal submucosal injectate. This trial will focus on polyps of size ≥ 11 mm removed by snare EMR technique. Patients with lesions deemed not suitable for EMR due to features suggestive of sub-mucosal invasion will not be included.

Injectate randomization:

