Study patients will be randomly assigned to the Eleview or the Hetastarch treatment group in a 1:1 ratio. Randomization will occur at the site using envelopes provided by the Investigator. The envelopes contents will specify the treatment assignment for each patient and opened by the research team (PI will be blinded).

We will monitor the safety and effectiveness data. The appropriate solutions will be injected into the submucosal space beneath the lesion(s) to be excised before the lesion(s) is/are removed. Subjects in both groups will receive the appropriate volume of injectate deemed necessary by the PI for the individual patient.

Objectives:

Primary objectives of the study are:

- To evaluate the effectiveness of Elevive injection in comparison to Hetastarch, for EMR. Effectiveness will be evaluated by the Sydney Resection Quotient (SRQ), which is defined as the size of the polyp divided by the number of pieces resected.
- To evaluate the safety of Elevive for EMR procedures in relation to adverse events and occurrence of complications during and after the EMR procedure in comparison to Hetastarch injectate.

Secondary objectives:

- To collect other effectiveness data regarding the administration of Elevive in comparison to Hetastarch, such as injectate amount required for efficient lesion lift and complete removal.

End-points:

Primary endpoints:

- Effectiveness of Elevive in comparison to Hetastarch for EMR in terms of:
 - Sydney Resection Quotient
 - Number of subjects with *en bloc* resection of lesions.
- Safety outcomes as assessed by complications during or after the procedures including:
 - Intra-procedural bleeding (bleeding requiring therapeutic intervention during the EMR).
 - Early (<24h) and delayed ($\geq 24h$ post EMR) post-procedural bleeding (bleeding post procedure that necessitates transfusion or endoscopic hemostasis because of hematemesis or a decrease of Hgb concentration of more than 2 g/dL after EMR).
 - Perforation

- Post-Polypectomy Syndrome
- Hospital admissions for any clinically relevant complications post-procedure.

Secondary endpoints:

➤ Effectiveness of Elevi[®] compared to Hetastarch in terms of:

- Injected volume needed for initial lesion lift
- Injected volume needed for complete removal of lesion
- Number of re-injections (number of times the injection device is passed down the scope).
- Number of resected pieces

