- Ease of use for polyp removal and fluid behavior combined, and rated on a 5-point scale for: very easy, easy, neutral, difficult and very difficult.
- Time (in minutes) to remove the lesion completely (measured from the first injection to final excision of the lesion), and total time of procedure.
- Need for additional treatments such as avulsion, coagulation or ablation.
- Pathological reports for negative lateral and/or deep margins (lateral margins only accurately assessed in *en bloc* resections)
- Presence and number of deep resections containing muscularis propria.
- *En-bloc* resections histologically examined for free-margins.
- Recurrent or residual neoplasia rates examined by biopsy (if applicable) at the follow-up visit.

Sample size and Statistical Analysis

At least 200 patients will be enrolled. 100 of these patients will be randomized to Elevi[®] injectate and 100 will be given the standard of care, Hetastarch injectate only. Efficacy and safety of Elevi[®] injectate has only been reviewed in one previous study. Therefore, the planned sample size was not calculated using a statistical power analysis, but was regarded as sufficient to repeat the objectives of the COSMO study (2017) and satisfy the exploratory purposes of the present study. Study personnel will carry out a simple randomization using a commonly used online generator. Randomization assignments will then be sealed until day of procedure until patient eligibility has been confirmed. The Principal Investigator will remain blinded and will perform all data analysis after completion of the study.

Data will be summarized and compared using classic descriptive statistics, i.e. mean, standard deviation, coefficient of variation (%), minimum, median and maximum values for quantitative variables, and frequencies for qualitative

variables.

The Sydney Resection Quotient will be compared between treatment groups using a Wilcoxon Rank-Sum test. The proportion of subjects with *en bloc* resection of all endoscopically visible lesions will also be compared between treatment groups using a Fisher's exact test. A nominal alpha level of 0.05 will be used for both the comparisons.

No formal comparison will be performed for the secondary endpoints.

Selection criteria

Inclusion criteria:

1. Sex and age: men and women > 18 years old
2. Subjects referred for EMR of polyps of size ≥ 11 mm
3. ASA score 1, 2 or 3.

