4. Contraception: Women of childbearing potential must have a negative pregnancy test (one is provided as the standard of care) or sign a waiver. Post-menopausal women must have been in that status for at least 1 year (per standard of care).
5. Subject is willing and able to participate in the study procedures and to understand and sign the informed consent

Exclusion criteria:

1. Age: Subjects is under 18 years old
2. Consent: Vulnerable subjects including those who are unable to consent
3. Pregnancy: Pregnant or breastfeeding women
4. ASA score <3
5. Physical findings: Abnormal physical findings that may interfere with the study objectives

Excluded lesions:

- Lesions less than 11 mm in largest dimension
- Lesions involving the muscularis propria (T2 lesions)
- Ulcerated depressed lesions (Paris type III) or pathology proven invasive carcinoma
- Proven malignant disease locally advanced or with metastasis
- Active inflammatory bowel disease lesion, e.g ulcerative colitis, Crohn's disease
- 6. Endoscopic appearance of invasive malignancy
- 7. Previous partial resection or attempted resection of the lesion
- 8. Allergy: Proven or potential allergic reaction to study products or history of anaphylaxis to drugs
- 9. Severe liver disease.

10. Known or suspected gastrointestinal obstruction or perforation, active diverticulitis, toxic megacolon,
11. Inflammatory bowel disease e.g ulcerative colitis or Crohn's disease
12. Hemostasis disorders (eg Von Willebrand disease, factor V Leiden thrombophilia or haemophilia), known clotting disorder (INR>1.5).
13. Subject with any other current serious medical conditions that would increase the risks associated with taking part in the study.
14. Patients must be advised to stop anticoagulation medications prior to the procedure per local practice guidelines and should re-start as clinically indicated after the procedure.

Visit 1 will be a screening appointment where the patient will be educated about the study and the informed consent document will be completed. The patient medical history will then be recorded, as well as current medications taken. The patient will also undergo a physical exam as standard of care. This visit can be combined with *Visit 2* (Day of Procedure).

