During *Visit 2*, inclusion and exclusion criteria will again be confirmed and after the lesion has been measured and found to be ≥ 11 mm and suitable for EMR, the patient will be randomized to the injectate. Polyps will be documented by photographic record prior to randomization. The injectate will be prepared out of sight from the investigator performing the EMR so that the investigator will remain blinded to the injectate. Patient vital signs including BP, HR and SpO2 will be recorded prior to, during, and after the procedure. Once the lesion has been injected, only Boston Scientific Captivator snares measuring 15-20mm will be used to resect the polyps, however additional treatment modalities required will also be recorded.

Visit 3 will consist of a follow up phone call 30 days ± 7 later. The occurrence or persistence of any adverse events will be recorded.

Data integrity and safety:

All paper charts pertaining to the patient will be kept under lock and key in coordinators office away from the endoscopy area. The data entry will be performed into an excel file which will be stored on an internal network drive with encryption and password security. Regular quality control checks of the data will be performed. Only approved personnel by the IRB will have access to the file storage. This file will also not have any identifiable information (name, DOB or

mrn). A study log with the identifiable information will be kept in a separate folder (also encrypted) to enable the investigators to assist in any research audit. No procedural data except the date of examination will be entered into this log. The data and safety will reviewed annually in addition to the continuous PI monitoring. Protocol revisions will be proposed, if needed, based on the results of the safety review including, but not limited to, stopping the randomization process.

References:

COSMO (2017). A randomized, double-blind, comparative, effectiveness and safety study of SIC 8000 in subjects undergoing Endoscopic Mucosal Resection (EMR) of colonic lesions equal to or larger than 2 cm

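### Does wording the en bloc test for all visible lesions let polyps outside the study decide a subject's result?

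*Combined protocol and SAP*

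**What the plan says.** The Fisher's exact test in Sample size and Statistical Analysis compares the proportion of subjects with en bloc "resection of all endoscopically visible lesions will also be compared between treatment groups". The list of primary endpoints names the same outcome more briefly: "Number of subjects with *en bloc* resection of lesions". Neither sentence carries a size limit, and the protocol nowhere defines a study lesion.

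The limit appears in other places:

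- Introduction: "This trial will focus on polyps of size ≥ 11 mm removed by snare EMR technique".
- Inclusion criterion 2: "Subjects referred for EMR of polyps of size ≥ 11 mm".
- Excluded lesions, first item: "Lesions less than 11 mm in largest dimension".
- Visit 2: the patient is randomised "after the lesion has been measured and found to be ≥ 11 mm and suitable for EMR".

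Visit 2 adds "Polyps will be documented by photographic record prior to randomization". Injectate randomization allows for more than one lesion per subject. Sample size and Statistical Analysis sets 100 patients per arm and a nominal alpha of 0.05 for each of the two comparisons. It also says that the number was not derived from a power calculation and that the purpose is exploratory.

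**The concern.** Being visible at endoscopy is a different criterion from being at least 11 mm and suitable for EMR. The protocol excludes small lesions but does not exclude subjects who also have them, so an enrolled subject may well have other polyps. On the literal wording, two analysts could score the same subject differently: one looks only at the lesion that brought the subject into the trial, the other at everything seen.

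At stake is the definition of success in one of the two formally tested outcomes. If extra polyps counted and their result did not depend on the arm, they would turn some successes into failures at the same rate in both arms. That would shrink a true difference and cost power.

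**Working it through.** **Step 1: the texts side by side.** The plan states no en bloc rate, effect size or power, so there is no figure of its own to reproduce. The main check is one of reading.

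| Place | Lesions covered |
|---|---|
| Title, Introduction | at least 11 mm |
| Primary endpoints | lesions, unqualified |
| Statistical analysis | all visible lesions, no size given |
| Inclusion criterion 2 | at least 11 mm |
| Excluded lesions | under 11 mm is out, at lesion level |
| Visit 2 | measured at 11 mm or more and suitable for EMR, before randomisation |

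The size exclusion is attached to lesions, so a lesion under 11 mm is most naturally outside the endpoint as well as outside the trial. No section says that small polyps are to be scored. The endpoint list and the analysis sentence do not contradict each other. The second adds something the first lacks: a rule for a subject with several lesions, namely that all must come out en bloc.

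**Step 2: how much the wide reading could matter.** Every rate below is an assumption. Let p be the en bloc rate for study lesions in an arm, q the share of subjects with an extra polyp, and r the chance that this polyp comes out whole, the same in both arms and independent of the study lesion. The scored rate is then

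p × (1 − q + q·r), and the share of successes reclassified is q(1 − r).

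Power is for the exact two-sided Fisher test, 100 per arm, alpha 0.05. The plan does not state sidedness; two-sided is assumed.

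| q | r | Factor | 20% vs 40% | 40% vs 60% | 60% vs 80% |
|---|---|---|---|---|---|
| none | – | 1 | 0.845 | 0.787 | 0.845 |
| 0.2 | 0.98 | 0.996 | 0.842 | 0.784 | 0.839 |
| 0.2 | 0.95 | 0.990 | 0.839 | 0.778 | 0.831 |
| 0.4 | 0.98 | 0.992 | 0.840 | 0.780 | 0.834 |
| 0.4 | 0.95 | 0.980 | 0.833 | 0.770 | 0.818 |
| 0.4 | 0.80 | 0.920 | 0.796 | 0.714 | 0.732 |

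Example of the factor: 1 − 0.4 + 0.4 × 0.98 = 0.992. In an arm of 100 with 60% en bloc, the number of subjects reclassified is 60 × 0.4 × 0.02 = 0.48 for r = 0.98 and 60 × 0.4 × 0.20 = 4.8 for r = 0.80.

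The last row, a loss of 5 to 11 points, needs one small polyp in five to come out in pieces. Visit 2 specifies that "snares measuring 15-20mm will be used to resect the polyps", which is wider than any polyp under 11 mm, so that row looks pessimistic.

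**Step 3: extra polyps that also receive the assigned fluid.** Injectate randomization puts no size limit on the lesions injected. Suppose q = 0.4 and the extra polyps respond to the fluid. The factor then differs by arm. With extra-polyp rates of 70% vs 85% and study lesions at 40% vs 60%, the scored rates are 0.40 × (0.6 + 0.4 × 0.70) = 0.352 and 0.60 × (0.6 + 0.4 × 0.85) = 0.564.

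| Extra-polyp rates | 20% vs 40% | 40% vs 60% | 60% vs 80% |
|---|---|---|---|
| 40% vs 60% | 0.829 | 0.792 | 0.850 |
| 70% vs 85% | 0.863 | 0.835 | 0.889 |

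Against the base row, the change runs from a loss of 1.5 points to a gain of about 5.

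**Step 4: no difference between arms.** With the same scored rate in both arms, the Fisher test rejects with probability 0.0363 at 40%, 0.0361 at 39.68% (40% × 0.992) and 0.0345 at 36.8% (40% × 0.92). All are below 0.05, so the wide reading does not inflate false positives at these rates.

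**The case for a change.** The strongest argument for acting is that the size limit has to be inferred. The analysis sentence uses its own criterion, visibility, and nothing in it points back to the eligibility section. An exploratory, unpowered study still has to fix who counts as a success. Nor need lesions outside the study be small: previously attempted lesions are also excluded, and the snare argument gives no comfort for a large one. If many successes were overturned the cost would be real. At 30% vs 50%, power would fall from 79% to 71% if 10% of successes were lost, and to 54% if 30% were.

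Part of this stands: a qualifier is missing. The rest is weaker. The layout of the exclusion list leaves open whether a previous attempt rules out the lesion or the subject; if the subject, the case cannot arise. The fall to 54% needs q(1 − r) = 0.30, for example q = 0.4 with r = 0.25, so that three extra polyps in four come out in pieces. Nothing in the documents suggests that.

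A tighter definition also brings choices the protocol does not settle. Counting only lesions marked before randomisation would drop an eligible lesion first seen afterwards. Requiring injection, or not, is a further open choice. Leaving injected small polyps out of the test loses information if they respond to the fluid: in one assumed case of Step 3, power goes back from 0.835 to 0.787.

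**Conclusion.** No change is needed. The analysis sentence omits a qualifier that the title, Introduction, inclusion criterion, excluded-lesion list and Visit 2 all supply. An analyst working from the whole protocol would score study lesions of at least 11 mm and take the word all as the rule for subjects with several of them. No stated figure is wrong and no stated power is missed.

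Even on the literal reading, the effect has no known size or sign. The assumed cases above run from a loss of 11 points of power to a gain of 5, with about 1 point or less lost when small polyps nearly always come out whole. These figures assume 100 per arm, a two-sided exact test, independence between lesions and invented values of q, r and the en bloc rates. They illustrate the mechanism and are not evidence of harm.

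### The inclusion and exclusion lists contradict each other on ASA score: classes 1 and 2 are both admitted and excluded, and only class 3 passes both lists

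*Combined protocol and SAP*

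**What the plan says.** The combined protocol and SAP mentions ASA score in two places, both under Selection criteria.

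- Inclusion item 3 admits patients with "ASA score 1, 2 or 3".
- Exclusion item 4 excludes patients whose ASA score is less than 3. It comes directly after the item "Pregnancy: Pregnant or breastfeeding women".

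Both lists are operative. The description of Visit 2 says that "inclusion and exclusion criteria will again be confirmed" on the day of the procedure, before the patient is randomised. The Sample size and Statistical Analysis section adds: "Randomization assignments will then be sealed until day of procedure until patient eligibility has been confirmed".

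The document does not rank one list above the other, and it gives no exception for ASA score.

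**The concern.** A patient must meet every inclusion criterion and no exclusion criterion. For a patient in ASA class 1 or 2, the two ASA lines give opposite answers, and staff checking eligibility at Visit 2 have no written basis for choosing between them.

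The stake is the definition of the study population. If staff follow the exclusion line, the trial is confined to ASA 3. If they follow the inclusion line, every ASA 1 or 2 patient they enrol meets a written exclusion. If different staff follow different lines, the enrolled population is a mixture that no one specified. Safety is one of the two primary objectives, so a reader of the complication rates needs to know which ASA range was meant to be studied.

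**Working it through.** There is no stated figure to reproduce. The point rests on no computed quantity, and on the sample size the plan says that "the planned sample size was not calculated using a statistical power analysis". The check is to apply the two criteria together.

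**Inputs**

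- Admitted by inclusion item 3: {1, 2, 3}.
- Removed by exclusion item 4 (ASA below 3): {1, 2}.
- Rule for combining them: both lists are confirmed before randomisation (Visit 2), so eligible = admitted minus removed.

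**Class by class**

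| ASA class | Inclusion item 3 | Exclusion item 4 | Result |
|---|---|---|---|
| 1 | admitted | excluded | contradiction |
| 2 | admitted | excluded | contradiction |
| 3 | admitted | not excluded | eligible |
| 4 and above | not admitted | not excluded | ineligible, through inclusion item 3 alone |

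**Results**

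- In conflict: {1, 2, 3} ∩ {1, 2} = {1, 2}, which is 2 of the 3 admitted classes.
- Eligible under both lists: {1, 2, 3} minus {1, 2} = {3}, which is 1 of 3.

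As written, exclusion item 4 acts only on classes that inclusion item 3 admits, and on none of the classes that item 3 leaves out.

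**Number of patients affected.** If a fraction p of the planned 200 patients (100 per arm) were ASA 1 or 2, then 200 × p of them would meet exclusion item 4. The document gives no ASA mix, so p may lie anywhere from 0 to 1 and the count anywhere from 0 to 200. The document cannot narrow that range.

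**Effect on the comparison.** ASA score is known before allocation, and the envelope stays sealed until eligibility is confirmed. Whichever line staff follow, the choice is made without knowledge of the arm. No endpoint or planned analysis uses ASA, and no alpha level or sample size changes.

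**The case against.** The strongest reply is that this is an obvious slip of one character. Inclusion item 3 names three classes explicitly, which would be an odd way to describe a trial meant for one. Some neighbouring exclusions look like negatives of inclusion items: exclusion items 1, 2 and 3 (age, consent, pregnancy) correspond to inclusion items 1, 5 and 4. Exclusion item 13 also removes any "Subject with any other current serious medical conditions that would increase the risks associated with taking part in the study", so an exclusion of the lower ASA classes runs against the rest of the list. On this view nobody would run the trial as an ASA 3 study.

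Much of this stands. A reversed sign is a plausible explanation, and a trial confined to ASA 3 is unlikely in practice. The parallel between the lists is only suggestive, however. The exclusions on vulnerable subjects and on breastfeeding go beyond the inclusion items they resemble, and excluding those under 18 does not exactly negate an inclusion of those over 18. No passage states the intent. A probable slip in an eligibility rule is still an error in a rule that staff must apply to every patient.

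A second reply is that the sign may have been misread when the PDF was converted to text. That cannot be ruled out from the text alone. Nothing shows it, though: the inequality signs for early bleeding (under 24 h), INR (above 1.5) and age (over 18) all read sensibly.

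A third reply is that the results do not depend on it. That is right for the comparison between arms and limits the weight of the point. It does not answer the question of who was eligible.

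**Conclusion.** The concern holds. Inclusion item 3 and exclusion item 4 contradict each other for two of the three admitted ASA classes, and a literal reading leaves only class 3 eligible. The conclusion needs no outside figure. It assumes only that the inequality sign in the source document is the one in the text reviewed, and that a patient must satisfy both lists.

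The consequence is an undefined eligible population, with either a narrower enrolment than inclusion item 3 describes or a deviation for each ASA 1 or 2 patient. It does not bias the randomised comparison. It should be fixed because it bears on every eligibility check, but it does not threaten the validity of the main analyses.

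**What to change.** The sponsor should first check the sign in exclusion item 4 against the source document, then state the intended ASA range and amend one line so that inclusion item 3 and exclusion item 4 define a single range. The reconciled wording should be the one used when eligibility is confirmed at Visit 2. The document does not show which item reflects the intent, so this review does not choose between them.

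If patients have already been enrolled, the sponsor should record which reading was applied, so that the report can describe the population and count any deviations on a stated basis.

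The amendment is one line and needs no extra patients, tests or visits.

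### The waiver allowed by inclusion 4 leaves the pregnancy exclusion without an objective check for untested women

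*Combined protocol and SAP*

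**What the plan says.** The relevant text is in the Selection criteria and the visit descriptions that follow them.

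- **Inclusion criteria, item 4:** "Women of childbearing potential must have a negative pregnancy test (one is provided as the standard of care) or sign a waiver". The two conditions are joined by *or*, so either is enough. The same sentence says that a test is already part of standard care.
- **Exclusion criteria, item 3:** "Pregnancy: Pregnant or breastfeeding women". The item is unqualified and does not say how pregnancy is to be established.
- **Visit 1 (screening):** "The patient medical history will then be recorded, as well as current medications taken", and "The patient will also undergo a physical exam as standard of care". The visit may be held together with Visit 2, on the day of the procedure.
- **Visit 2 (day of procedure):** before randomisation, "inclusion and exclusion criteria will again be confirmed". No pregnancy test is named.
- **Visit 3:** a telephone call at about 30 days to record adverse events. It does not mention pregnancy.

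The available text does not describe the content of the waiver.

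**The concern.** One criterion undercuts another. Exclusion 3 is a firm bar, and the only objective check on it anywhere in the plan is the test in inclusion 4. That item makes the test optional. A woman who takes the waiver route satisfies inclusion 4 untested, and no later step supplies what the test would have shown.

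What is at stake is eligibility and participant protection. Staff could follow every written step and still randomise a woman whom the protocol means to exclude. The plan describes no step that would bring this to light afterwards. The waiver may serve a purpose in routine care, but here it is a condition of entry to a comparison whose primary objectives include safety.

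**Working it through.** The plan states no figure on this point, so there is none to reproduce. The check sets the criteria and visits side by side.

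**Step 1: the two routes through inclusion 4**

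| Route | Inclusion 4 met? | What supports exclusion 3 (pregnancy) |
|---|---|---|
| Negative test | Yes | Test result, plus self-report, history and examination |
| Signed waiver, no test | Yes | Self-report, history and examination only |

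**Step 2: does a later step close the gap on the second route?**

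- Visit 1: history and examination can reveal a known or clinically evident pregnancy. They cannot be relied on to reveal one that the woman does not know of and that shows no signs.
- Between visits: Visits 1 and 2 may fall on the same day, so there need be no interval in which her status becomes known.
- Visit 2: repeating the eligibility check repeats the same information. The signed waiver confirms inclusion 4, and exclusion 3 is judged again on report, history and examination.
- Visit 3: the call comes after treatment and is described only in terms of adverse events.

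No step after the waiver adds an objective check. What can pass is narrow: a woman who is untested, and whose pregnancy is both unrecognised and not clinically evident.

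**Step 3: how many women might enter untested**

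The documents give only the planned enrolment, at least 200. The other two inputs are assumptions.

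- Share of patients who are women of childbearing potential: 5% to 10% (assumed).
- Share of those who sign the waiver: 10% to 50% (assumed).
- Formula: untested entrants = enrolment × share of childbearing potential × waiver share.
- Low end: 200 × 0.05 × 0.10 = 1.
- High end: 200 × 0.10 × 0.50 = 10.

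This range counts women for whom exclusion 3 has no objective check. It does not count pregnancies. Those would be a small fraction of it, and the documents give nothing from which to estimate that fraction.

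**The case against.** The best case for the plan has four parts.

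- **The criteria apply jointly.** Signing a waiver satisfies inclusion 4 but does not switch off exclusion 3. A reported or evident pregnancy still excludes the woman, and eligibility is checked again before randomisation. This stands. A reader might infer that exclusion 3 cannot be applied to waiver signers, or that no pregnancy among them would be detected. The documents do not support either inference: the exclusion still operates, but without an objective check.
- **The waiver's content is unknown.** It could be a refusal of testing, a statement that she is not pregnant, or an acceptance of risk. Consent pages are not in the public file and might contain its wording. This also stands, so it would be wrong to say that the waiver carries no information. Even a statement that she is not pregnant, however, is self-report and cannot reveal a pregnancy she does not know of.
- **The added risk is not shown.** The Introduction says that Eleview is FDA-approved, the sample size section calls hetastarch the standard of care, and participants are already referred for EMR. The documents say nothing about pregnancy risk with either injectate. A reader might infer a demonstrated participant-safety failure, and the text does not establish one. But the protocol itself chose to exclude pregnant women, and it notes that Eleview's efficacy and safety have been examined in only one earlier study. Having set the exclusion, it should say how it is verified.
- **The exclusion is wider than the gap.** It also covers breastfeeding women and women who know they are pregnant. A pregnancy test does not bear on the first group, and the second is excluded by report. This is correct and limits the point to unrecognised pregnancy.

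**Conclusion.** The point holds in a limited form. Inclusion 4 accepts a waiver in place of a test, exclusion 3 bars pregnant women, and nothing else in the text requires a test or defines the waiver. For untested waiver signers the exclusion is unverified, though not inoperative, and a woman with an unrecognised pregnancy could be randomised with no departure from the plan.

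The number affected is probably small: 1 to 10 untested women in 200 under the assumed ranges, and fewer pregnancies than that. The conclusion does not depend on those ranges, because it follows from the wording of the criteria and the visit descriptions. It does assume that no test is made compulsory in material outside the public file.

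No endpoint, test or alpha level is affected. This is an eligibility and participant-protection gap that should be corrected, not a threat to the analysis.

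**What to change.** Reconcile inclusion 4 with exclusion 3 for the purpose of trial entry. If exclusion 3 stands, delete the waiver alternative from inclusion 4, so that the eligibility of women of childbearing potential rests on the test already provided. A woman who prefers the waiver keeps it for her routine care and is not randomised. This changes who enters the trial and leaves clinical care as it is. It would also help to name the pregnancy check in the Visit 1 or Visit 2 description, so that the eligibility confirmation refers to a recorded result.

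The cost is one phrase in the criteria and no new procedure. The downside is the loss of the few women who would choose the waiver. The documents do not give their number; under the ranges assumed above it is 1 to 10 of 200. That loss would not disturb a power target, because "the planned sample size was not calculated using a statistical power analysis", and enrolment is stated as a minimum, so the places could be filled by others.
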